Accordingly, additional rigorously controlled studies are required to determine if iTBS-TMS is an effective treatment for Veterans with AUD.

This is double-blind placebo controlled project will deliver completely novel data on the efficacy of iTBS-TMS to promote sustained abstinence for Veterans with AUD during the first 6 months following treatment. Monthly monitoring over the entire first 6 months following treatment is crucial, given relapse within the first 6 months of treatment is robustly related to poor psychosocial functioning over the ensuing 1-3 years. The ultimate goal of this proposal is to provide treatment that more effectively promotes sustained

abstinence in the Veteran with AUD, as extended abstinence is robustly associated with optimum biomedical, neuropsychological, psychiatric, and psychosocial recovery and functioning.

c) Explain why human subjects must be used for this project. (i.e. purpose of study is to test efficacy of investigational device in individuals with specific condition; purpose of study is to examine specific behavioral traits in humans in classroom or other environment)

The goal of this study evaluate the efficacy of iTBS-TMS as a treatment for Veterans with an AUD; therefore, humans must be studied.

2. Study Procedures

a) Please SUMMARIZE the research procedures, screening through closeout, which the human subject will undergo. Refer to sections in the protocol attached in section 16, BUT do not copy the clinical protocol. Be clear on what is to be done for research and what is part of standard of care.

PROTOCOL SUMMARY:

1. Recruitment and screening: Participants will be recruited via VA Palo Alto HCS Addiction Treatment Services.

2. Informed Consent: Prior to consent, The PI, or Co-PI or research assistant or qualified RA, will recheck inclusion/exclusion criteria.

3. Baseline/Pretreatment Assessment:

- Psychiatric Assessment
- Alcohol and Substance use
- Neurocognitive Assessment
- 3 Tesla Magnetic Resonance Neuroimaging
- Blood draw (as described in DETAILS OF RECRUITMENT, DESIGN AND TREATMENT below)

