Recruitment and screening: Potential participants from the VA Palo Alto treatment programs will be identified based on VA medical/clinical staff diagnoses of an alcohol use disorder without any comorbid condition any conditions that be contraindicated for study (e.g., taking medications that lower seizure threshold, magnetic resonance neuroimaging contraindications, medically confirmed seizure disorder). Specifically, medical/clinical staff of the programs listed above will identify potential participants who meet eligibility criteria and inform the patient that a research opportunity is available to them and offer contact information to study personnel or the participant may request that study personnel contact them. The study has been explained to clinicians via treatment team meetings, so they are familiar with eligibility criteria. The PI, Co-PI or qualified RA will check inclusion/exclusion criteria based on initial eligibility and sociodemographic data via in person screen at the treatment program or at the MIRECC, Building 5, 4th floor. Private interview rooms are available for this purpose at both locations.

Baseline/Pretreatment Assessment (see section 2.a.3.b. of grant application):

- a) Psychiatric Assessment: will use standardized measures employed in clinical practice and research.
- b) Alcohol and Substance use: will use standardized measures employed in clinical practice and research.
- c) Neurocognitive Assessment: will use standardized measures employed in clinical practice and research
- d) 3 Tesla Magnetic Resonance Neuroimaging: will be conducted at the Stanford Center for Neuroimaging.
- e) Blood draw A venipuncture of the arm be performed and maximum of 20 ml of blood will taken by trained nursing staff or trained phlebotomists in the VA Palo Alto Clinical Research (CCR), main hospital building 100. [name] will obtain participants' blood samples from the CCR and deliver them to the VA-MIRECC Genetics Laboratory for DNA extraction and genotyping and VA-MIRECC Translational Laboratory, where she will conduct biomarker analyses. These labs are located in Building 7 at VAPAHCs.

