Design, Treatment Phase and Treatment Arms: This is a double-blind randomized group design, which will enroll 40 participants. After screening and baseline procedures, participants will be randomized to active or sham iTBS-TMS conditions (20 active, 20 sham); thus participants will have a 50% probability of receiving active treatment. Participants will receive 20 iTBS-TMS sessions over the course of 2 weeks. Participants will be required to be abstinent from alcohol and illicit substance for 7 days and demonstrate no clinically significant withdrawal symptoms prior to randomization.

Rationale for Brain Region Site: The left dorsolateral prefrontal cortex (DLPFC) was chosen as the iTBS stimulation site given excitatory transcranial magnetic stimulation to this region has been demonstrated to decrease cravings in non-Veterans with AUD. Additional stimulation of this site has been robustly shown to be associated with decreased unipolar depressive symptomatology; depressive disorders are highly comorbid in Veterans with AUD.

Duration of Treatment Phase: Active iTBS-TMS Treatment Group – will receive a total of 20 treatments delivered 5 days/week, two treatments per day (Monday-Friday), over 2 consecutive weeks. Sham Treatment group will receive the same frequency and

duration of treatment, without actual administration of iTBS-TMS. iTBS-TMS sessions will be delivered prior to the beginning of participants' treatment day, and at lunch, as to not interfere with their treatment-as-usual in the VA substance treatment clinics. There have been no adverse events reported in the literature implementing two iTBS sessions per day in any population.

Procedures for Delivery of iTBS-TMS Sessions:

1) Anatomical localization of the left DLPFC for the stimulation coil will be individualized for each participant and achieved through standardized procedures for EEG electrode placement, optimized for transcranial magnetic stimulation. The localization of participant left DLPFC will be confirmed using the subject MRI data collected prior to the treatment phase.

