2) Motor Threshold (MT) Elicitation: Inherent to the safe and accurate dosing of TBS stimulation, active MT elicitation will be performed according to established protocols, which have been in use since 1994. This protocol is well-established as an effective method for MT Elicitation, widely implemented within both sham-controlled transcranial magnetic stimulation research with demonstrated safety. MT will be calculated for all participants prior to randomization.

3) iTBS-TMS Dosing: Dosing of iTBS-TMS will = 100% of the active MT adjusted to the skull to cortex distance (via each participants structural MRI), as this is documented to modulate the desired cortical target, and is not associated with any adverse events. Six

hundred (600) pulses of iTBS-TMS at 50 Hz will be utilized, consistent with standard parameters. There will be 10 trains of 3 pulses at 50Hz every 200ms (50Hz over 5Hz), which is 30 pulses per theta burst train. Twenty (20) trains will be delivered to achieve 600 pulses over approximately 3 minutes.

4) Sham Control and Blinding Methods: The sham-control and blinding methods will be the same as used in TMS trials in which investigator and participant blinding to group assignment was carefully documented and achieved in previous clinical trials conducted with Veterans at VA medical centers. These methods involve: (a) the Cool-B65-Active/Placebo Coil, which functions as both an active and sham coil; (b) scalp electrodes; and (c) a white-noise generator. The scalp electrodes are used to pass a low-voltage, low electric current (2–20mA at no more than 100V) to mimic the sensation of receiving actual iTBS. The white-noise generator is used to send low-volume white noise to the subject's ears when magnetic stimulation pulses are initiated to hide the click noise the iTBS-TMS produces.

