
Additional Procedures for the Monitoring of Seizures and Suicidal Ideation/Behavior:

Screening, Baseline and Treatment Phase: In the unlikely event that a seizure does occur, participants will be closely monitored and treated for any medical or psychological consequences. rTMS sessions will be conducted at the VA Palo Alto MIRECC, which fully equipped to safely handle a seizure. If at any point during study participation, a participant has a seizure, the participant will be withdrawn from the study immediately (although they will still be followed for protocol assessments). All seizures will be considered serious adverse events (SAE) and as such, will be reported to the study PI. We will immediately suspend enrollment if 10 participants experience a seizure during study participation, and request that the Data Monitoring Committee (DMC) evaluate the SAE data, to determine if enrollment of new participants should be resumed without protocol changes, if protocol modifications should be made before resuming enrollment, or if the study should be terminated. We recognize that study termination or modification based on SAEs, such as seizures, ultimately rests with the DMC and the study PI.

If a participant expresses suicidal ideation/intent, and is determined to be a risk to self, a clinical evaluation will be immediately conducted by the PI (a licensed clinical psychologist), Co-Is (a licensed clinical psychologist or board certified psychiatrist), by the participant's individual mental health provider, and/or a mental health emergency clinician. The participant will remain with qualified study personnel or a MIRECC clinician until the evaluation has been completed and a decision made about disposition in conjunction with the Chief of Mental Health Outpatient Clinic or the emergency mental health clinician.

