Reporting: In this study, all ADEs and AEs that occur during the acute treatment and follow-up phases will be collected and followed until resolution or the individual's participation in the study ends. All events will be recorded on the appropriate case report form. "Relatedness" involves an assessment of the degree of causality between the study intervention and the event. PIs will be asked to provide an assessment of relatedness. The assessment provided by the PI is part of the information used by the sponsor to determine if the adverse event or effect presents a participant safety concern. An ADE is deemed to be associated with the use of the study device if there is a reasonable possibility that the experience may have been caused by the device or by participation in the trial. Thus, all adverse events or effects with a reasonable causal relationship to the rTMS treatment should be considered related. A definite relationship does not need to be established. The following levels of relatedness will be used in this study:

- Not attributed to the iTBS-TMS treatment
- Possibly attributed to the iTBS-TMS treatment
- Attributed to the iTBS-TMS treatment

Serious Adverse Events (SAEs) and Unanticipated Adverse Device Effects (UADEs)

Definitions:

Serious Adverse Events (SAEs) are a subset of adverse events and are defined by the ICH for Clinical

Safety Data Management as any untoward medical occurrence that:

- Results in death
- Is life-threatening
- Requires inpatient hospitalization or prolongation of existing hospitalization
- Results in persistent or significant disability or incapacity
- Is a congenital anomaly/birth defect or
- Any other condition that, based upon medical judgment, may jeopardize the subject and require medical or surgical treatment to prevent one of the above outcomes.

An Unanticipated Adverse Device Effect (UADE) is defined as: Any serious adverse effect on health or safety or any life-threatening problem or death caused by, or associated with, a device, if that effect, problem, or death was not previously identified in nature, severity, or degree of incidence in the investigational plan or application, or any other unanticipated serious problem associated with a device that relates to the rights, safety or welfare of participants. For this study an UADE is considered a category of SAE, which will be reported on the same form.

Collection and Recording

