For this study, all SAEs and UADEs will be recorded on the SAE form, regardless of cause. The PI will be asked to determine whether the serious adverse event is related to:

- iTBS-TMS device
- iTBS-TMS treatment
- Medications used to treat AUD and/or co-occurring conditions

Collecting and recording SAEs/UADEs will begin at randomization and will continue throughout the follow-up phase. For a participant who ends study participation prior to the study's completion date, unresolved SAEs will be monitored and reported for 30 days after the End of Study date for that participant. In addition, the investigator must collect all SAEs reported to them for a period of 30 days after the study's completion.

Expedited Reporting of Serious Adverse Events (SAEs) and Unanticipated Adverse Device Effects (UADEs)

Study personnel will be responsible for initially evaluating all serious adverse events for participant safety concerns and will confer with the PI as required during this evaluation process. After being reviewed by the PI, any event deemed to be related, serious and unexpected will be reported to study investigators.

Expedited Reporting by the Sponsor to the FDA: PI will review the SAE report to assess completeness of documentation and to determine whether the SAE requires expedited reporting to the FDA. Specifically, if an event meets the criteria for unexpectedness (i.e., not previously reported) and seriousness it will be reported as required by regulation to the FDA within 10 working days for UADEs and within 7 calendar days for unexpected SAEs (Safety Reports) of the sponsor receiving the report as required by regulation.

Data Monitoring Committee (DMC): Reporting of Adverse Events, Adverse Device Effects, Serious Adverse Events, and Unanticipated Adverse Device Effects. Study Personnel will generate tabulations of AEs and SAEs and present a summary of these to the DMC on a schedule set by the DMC. The DMC will also determine when they should be unblinded to treatment assignment for the reviewing of adverse event data. The DMC will advise the PI concerning whether the study should continue or be stopped for safety reasons. Note: We request that a DMC be assigned to us by our VA granting agency.

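### SAE/UADE recording starts at randomization and AE/ADE collection at treatment, after consented participants have had motor-threshold elicitation, 3T MRI and a blood draw; for seizures this also conflicts with the plan's own seizure rule

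*Combined protocol and SAP*

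**What the plan says.** Two rules in Section 9(c) set the recording windows.

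- Serious events (Collection and Recording): "Collecting and recording SAEs/UADEs will begin at randomization". The window then runs through follow-up.
- Other events (Adverse Events and Adverse Device Effects, Reporting): "all ADEs and AEs that occur during the acute treatment and follow-up phases will be collected". Baseline is not named.

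Section 2(a) sets the order of procedures.

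- Design, Treatment Phase and Treatment Arms: "After screening and baseline procedures, participants will be randomized to active or sham iTBS-TMS conditions".
- The Baseline/Pretreatment Assessment list in the Protocol Summary includes "3 Tesla Magnetic Resonance Neuroimaging" and a blood draw. The detailed description puts the draw at a "maximum of 20 ml of blood will taken by trained nursing staff or trained phlebotomists".
- Procedures for Delivery of iTBS-TMS Sessions, item 2: "MT will be calculated for all participants prior to randomization".

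The seizure and suicidality procedures in Section 9(c) have a wider window. Under a subheading that names screening, baseline and treatment, they class all seizures as SAEs to be reported to the PI. The withdrawal rule there opens "If at any point during study participation, a participant has a seizure", and the trigger for suspending enrollment (10 participants with a seizure) also counts over study participation. The same subheading requires immediate clinical evaluation of a participant judged to be a risk to self.

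Section 9(e) adds that SAEs are reported within 24 hours of being learned of and unanticipated problems within 5 days. It gives no start date for either.

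**The concern.** Followed as written, the recording rule leaves a serious event at the baseline MRI, blood draw or motor-threshold session off the SAE form, because the form's window has not yet opened. A person who consents, has such an event and is therefore never randomized has no stated SAE recording at any point.

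The downstream uses depend on these records. Section 9(c) has study staff tabulate AEs and SAEs for the Data Monitoring Committee, and has the PI review the SAE report to decide on expedited reporting to the FDA. A record that opens after the first procedures can feed incomplete information into both.

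The motor-threshold step deserves most attention. If it delivers pulses from the study device, it is each participant's first exposure to stimulation. Because the sham arm is described as receiving no actual iTBS-TMS, it would also be the only active stimulation for 20 of the 40 participants.

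**Working it through.** No sample size, power or error rate is involved, and the plan gives no figure to reproduce. The check sets the order of procedures against the recording windows and then looks for text that closes the gap.

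**Step 1: order of events.** From Sections 2(a), 9(c) and 13:

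1. Screening interview, then written consent before any study procedure (Section 13.2, rationale).
2. Baseline assessments, 3T MRI, blood draw and motor-threshold elicitation. The order among these is not stated.
3. Randomization. SAE/UADE recording opens.
4. Treatment phase. AE/ADE collection opens.
5. Follow-up. Both windows continue.

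Everything in item 2 happens after consent and before either window opens.

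**Step 2: is motor threshold a use of the device?** Section 2(a) says that active motor-threshold elicitation is performed and that it underlies dosing, but it does not describe the pulses. Device exposure is inferred from the name and purpose of the step. The MRI and blood-draw part of the point does not need this inference.

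**Step 3: consistency with the plan's own definitions.** Section 9(c) defines an AE as an untoward occurrence in a person participating in research, and has all SAEs and UADEs recorded whatever their cause. A consented person at baseline meets that definition but falls outside the window. The MRI and blood draw are repeated after treatment (Section 2(a), Post-Treatment Phase), so the same serious event would go on the SAE form at the second occasion and not at the first.

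**Step 4: does other text close the gap?**

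- *Seizures.* The seizure procedures cover screening and baseline and make every seizure an SAE. They do not name the SAE form or change its start date. The suspension trigger thus counts over all of participation, while the SAE record that would supply the count opens at randomization. These two rules conflict.
- *Suicidal crisis.* Clinical evaluation at baseline is required. That is care, not recording.
- *Other serious events.* The 24-hour and 5-day rules in Section 9(e) are deadlines for reporting. They do not say from when events are collected.
- *Attribution.* The relatedness question in Collection and Recording offers device, treatment and medications. It has no category for MRI or blood draw.

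**Step 5: how many events?** The documents give no expected number before randomization. Section 9(a) puts TMS seizures below 1% without stating the denominator. If that is read as per participant, the expected number is below 40 × 0.01 = 0.4 over the whole trial, and the baseline part is smaller still. Section 9(a) also reports no serious adverse events during scanning at the imaging center. Few events are likely.

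**The case against.** The strongest reply is that baseline is not a safety blind spot. Seizure, which Section 9(a) names as the primary TMS safety concern, is covered from screening onward: every one is an SAE, goes to the PI, and counts toward a suspension with committee review. Suicidal risk at baseline brings immediate evaluation. Section 9(e) requires SAEs to be reported within 24 hours and unanticipated problems within 5 days, with no limit to the period after randomization, and has the board review both along with protocol deviations. The Confidentiality Protections list adverse effects during the study among the research data. The FDA reporting paragraph sets no start date of its own. Finally, events before randomization precede any iTBS session and cannot bias active versus sham.

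Much of this stands. A reader might infer that no baseline event would reach any tabulation, or that the seizure procedures are the only cover and stop at the PI. The documents do not support either reading: the seizure procedures also address suicidality and reach the monitoring committee, and the Section 9(e) routes are open in time.

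A reader might also size the gap from the participation-time table in Section 8(m), where baseline takes 6.5 of about 22.5 hours. That is not a valid measure. Hours are not risk, much of baseline is interviews and testing, and the table does not say where motor threshold falls.

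What the reply does not do is open the SAE form earlier. A deadline that runs from learning of an SAE leaves unclear whether an event before the stated recording start is handled as one. The unanticipated-problem route need not capture a serious event of an expected kind. The FDA paragraph works from the SAE report, which the recording rule does not call for before randomization.

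**Conclusion.** The point holds in a limited form and should be corrected. For seizures, Section 9(c) contradicts itself on when recording applies. For other serious events between consent and randomization, the plan states no routine SAE recording, only general reporting deadlines. Non-serious events in that period are also outside the stated collection window.

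The consequence is possible incompleteness of the monitoring committee's tabulations and of the SAE reports reviewed for the FDA. All 40 planned participants pass through the window, together with an unstated number who consent and are not randomized; the latter group is the most exposed. The number of events lost cannot be estimated from the documents and is probably small.

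The efficacy analysis and the between-arm safety comparison are not biased, since the events precede allocation. The conclusion rests on reading the recording rule literally. For the motor-threshold part alone, it also rests on the inference that this step uses the study device.

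**What to change.** - In Section 9(c), Collection and Recording, start SAE/UADE recording at signed informed consent in place of randomization.
- In Section 9(c), Adverse Events and Adverse Device Effects, Reporting, add the baseline phase to the AE/ADE collection window.
- Tabulate pre-randomization events in a separate table with all consented participants as the denominator, showing who was and was not later randomized. Keep the by-arm tables to events after randomization.
- Reconcile the seizure procedures, the two recording rules and the reporting deadlines in Section 9(e), so that all use the same start and the suspension trigger draws on a record covering the same period.

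The cost is a few sentences and a few additional case report forms. A participant ID is already assigned once consent is signed (Confidentiality Protections, item f), so no new system is needed. No treatment procedure, sample size or efficacy analysis changes.

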If a medical adverse event should occur, study staff includes two physicians who are board-certified in psychiatry (Drs. [name] and [name]). Additional medical assistance will be available through the VA TMS clinical roll-out staff RN's and physicians trained in TMS safety and adverse event management, and VA Palo Alto HCS Emergency Department service is readily available, if needed. Immediate psychiatric/psychological consultation will available for participants if required ([name]: Licensed Clinical Psychologist and [name]: Board Certified Psychiatrist). Appropriate referrals will be made when necessary in the judgment of the PI/PD or study physician.

g) Lead Investigator or Coordinating Institution in Multi-site Study.

Please explain (i) your role in coordinating the studies, (ii) procedures for routine communication with other sites, (iii) documentation of routine communications with other sites, (iv) planned management of communication of adverse outcomes, unexpected problems involving risk to participants or others, protocol modifications or interim findings.

1. Purpose

a) In layperson's language state the purpose of the study in 3-5 sentences.

The purpose of this study is to evaluate the efficacy of intermittent theta burst (iTBS) transcranial magnetic stimulation (TMS) as a treatment for Veterans with an alcohol use disorder (AUD) to decrease the exceedingly high rate of relapse associated with this condition.

b) State what the Investigator(s) hope to learn from the study. Include an assessment of the importance of this new knowledge.

At least 60% of those with AUD will experience a major relapse period within 6 months of treatment, irrespective of the intervention

(psychosocial and/or pharmacological) employed. Consequently, the high prevalence of AUD and relapse following treatment in Veterans is associated with substantial resource allocation and costs for the DVA Health Care System. Current pharmacological and psychosocial interventions demonstrate only a moderate level of efficacy, which is reflected in the high rate of relapse in AUD.

iTBS-TMS is a neurostimulation method that is at the forefront of innovative, non-invasive, and safe treatments for AUD, and the disorders that commonly co-occur with AUD. To reduce the high rate of relapse in Veterans with AUD, it is necessary for interventions to more effectively address the associated neurobiological dysfunction and salient co-occurring conditions.

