Statistical Approach: Primary Hypothesis 1a will be tested with binary logistic regression. The criterion/dependent measure is relapse status (abstained or relapsed during the 6 months after last iTBS-TMS session). Treatment group (active iTBS-TMS vs. control) is the target predictor, and covariates will include age and composite neurocognitive functioning (based on demographically adjusted RBANS total score) as these variables may account for both within and between subject group variance. PTSD severity (based on PCL-5 total score), substance use severity (based on NIDA Drug Survey composite score), depression severity (based on BDI total score), and/or smoking severity (based on pack-years) will be considered as covariates if, after random assignment, there are post-hoc differences between treatment groups on these variables following breaking of the blind.

1b) Veterans who receive active iTBS-TMS treatment for AUD will demonstrate a significantly greater duration of abstinence in the 6 months following treatment than controls.

Statistical Approach: Primary Hypothesis 1b will be tested with Cox regression. The criterion/dependent measure is duration of abstinence after final iTBS-TMS session, and covariates include those listed for Primary Hypothesis 1a.

Secondary Hypothesis:

In the active iTBS-TMS group, Veterans with: (a) lower Glu concentration, (b) lower perfusion (blood flow), and (c) smaller volume of the left DLPFC at baseline will demonstrate a longer duration of abstinence over 6 months post treatment.

Confirmation of this hypothesis will indicate that participants who exhibit lower baseline Glu concentration, lower perfusion (blood flow), and/or smaller left DLPFC volume, and receive active iTBS-TMS, demonstrate the most robust iTBS-TMS treatment response because iTBS-TMS addresses these key neurobiological deficits that are associated with increased relapse risk. Confirmation of this hypothesis will advance our understanding of the neurobiological characteristics that predict the greatest benefit from iTBS-TMS at entry into treatment for AUD.

Statistical Approach: The Secondary Hypothesis will be tested with generalized linear mixed modeling or linear mixed modeling, depending on the distribution of the dependent measure. Duration of abstinence is the dependent measure.

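### Primary 1a fits ordinary logistic regression to 40 people, which on average exaggerates a real treatment odds ratio; a penalised fit removes nearly all of this at little cost.

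*Combined protocol and SAP*

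**What the plan says.** Protocol section 2(a), under Design, Treatment Phase and Treatment Arms, states that "participants will be randomized to active or sham iTBS-TMS conditions (20 active, 20 sham". In the Statistical Analyses Plan, under Primary Hypothesis 1a, "Primary Hypothesis 1a will be tested with binary logistic regression". On the outcome: "The criterion/dependent measure is relapse status (abstained or relapsed during the 6 months after last iTBS-TMS session". On the treatment term: "Treatment group (active iTBS-TMS vs. control) is the target predictor". Two adjustment variables always enter beside it: "covariates will include age and composite neurocognitive functioning (based on demographically adjusted RBANS total score".

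Four further scores (PTSD, substance use, depression and smoking severity) "will be considered as covariates if, after random assignment, there are post-hoc differences between treatment groups on these variables". The plan gives no threshold for a difference.

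The SAP does not name a penalised or exact method, does not choose between Wald and likelihood-ratio tests, and does not say what happens if the fit fails to converge. Its remarks on overfitting cover the separate neuroimaging models under the Secondary Hypothesis and the latent-variable models under Tertiary Analyses. Primary 1a has none.

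The only relapse rate in the documents is background, in section 1(b): "At least 60% of those with AUD will experience a major relapse period within 6 months of treatment".

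**The concern.** Maximum-likelihood logistic coefficients are biased away from zero when the smaller outcome class is small relative to the number of coefficients. A 40-person trial with a binary primary outcome and at least three coefficients is in that range. The reported odds ratio would then tend to look better than the true one whenever there is a real effect. If software reports a likelihood-ratio p-value, it would also run slightly too small.

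The estimate matters because section 3(a) expects the work to give VA clinicians preliminary data for decisions about the usefulness of the treatment. It would also be a natural input to the sizing of a later trial. Exploratory 1a and 2a use the same method in subsets of the same 40 people, where counts are smaller still.

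**Working it through.** **Inputs from the documents.** N = 40, 20 per arm. Fixed terms: treatment, age, RBANS, so 1 + 2 = 3 coefficients (intercept not counted). Conditional terms: up to 4, so at most 3 + 4 = 7. Background relapse: at least 60%.

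**Assumptions, because the documents give no figure.** Two-sided 5% level; sham relapse 60%; active relapse 40% or 30% when treatment works; covariates independent and standard normal, with log odds ratios per SD between 0 and 0.5. The plan gives no power calculation, so there is no figure of its own to reproduce.

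**Smaller outcome class.**
- No effect, 60% relapse in both arms: 0.40 × 40 = 16 abstainers; 16/3 = 5.3 per coefficient, 16/7 = 2.3.
- 60% v 30%: 12 + 6 = 18 relapses expected; 18/3 = 6.0, 18/7 = 2.6. The simulated mean of the smaller class is about 17.

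**True effects.** For 60% v 30%: ln(0.30/0.70) - ln(0.60/0.40) = -0.847 - 0.405 = -1.25, odds ratio 0.286. For 60% v 40%: -0.405 - 0.405 = -0.81, odds ratio 0.444.

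**Simulation.** Trials were generated under these assumptions and fitted by maximum likelihood and by Firth penalised likelihood. There were 20,000 trials per setting for the main no-effect runs and 2,500 to 4,000 for the others.

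| Terms in model | Exaggeration of log odds ratio when treatment works | Likelihood-ratio type I error | Wald type I error |
|---|---|---|---|
| 3 (always fitted) | 11 to 16% | about 6% | 4.4 to 5.3% |
| 5 | 21% or more | 7.3% | 5.6% |
| 7 (all scores added) | 34 to 48% | about 8 to 10% | about 5 to 6% |

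- Three terms, 60% v 30%: mean -1.42, and 1.42/1.25 = 1.14, so 13 to 14% too large. The mean corresponds to an odds ratio of exp(-1.42) = 0.24 against 0.286. The median is also too extreme, at about -1.37 to -1.40, so a few extreme fits do not explain it.
- Three terms, 60% v 40%, covariates without effect: the mean corresponds to an odds ratio of 0.405 against 0.444, and ln(0.405)/ln(0.444) = 1.11.
- No effect: mean log odds ratio between -0.005 and 0.008 in every setting, so there is no bias under the null.
- Likelihood-ratio test, three terms: 6.0% in the 20,000-trial run. Most smaller runs gave 5.8 to 6.1%; one set of 3,000-trial runs gave 7.0 to 7.3%.
- Separation or non-convergence: under 0.1% of trials with three terms; under 1% in most seven-term runs and up to 2% in one.

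**Firth fit on the same kind of data.**
- Three terms, 60% v 30%: mean -1.25 to -1.27.
- Root mean squared error, three terms: 0.86 falls to 0.73. From these rounded figures, (0.86 - 0.73)/0.86 = 15%; about 16% before rounding.
- Type I error of the penalised likelihood-ratio test: 4.4 to 5.0% with three to seven terms.
- Power, three terms, 60% v 30%: Firth about 43 to 46%, Wald about 44 to 47%, ordinary likelihood-ratio about 48 to 50%.

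**How likely is the seven-term model?** The plan gives no imbalance threshold. If it were p < 0.05 with independent scores, all four would enter with probability 0.05⁴ = 0.000006, and none would enter with probability 0.95⁴ = 0.81. At p < 0.20, all four would enter with probability 0.20⁴ = 0.0016. Correlated scores would raise these figures. With the p < 0.05 rule itself simulated, the model averaged 3.2 coefficients, no trial of 4,000 reached seven, and the mean log odds ratio was -1.37 (about 9% too large).

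**The case against.** The strongest objection is that the bias is small beside the uncertainty of a 40-person trial. With three terms the estimate has a standard deviation of about 0.85, so a bias of about 0.17 is 0.17/0.85 = 0.2 standard deviations, and nominal 95% Wald intervals cover 95.2%. This stands, and it is why the point is an improvement and not a defect that invalidates the analysis. It does not remove the case for Firth, which lowers variance as well as bias.

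A reader might infer that the plan's p-values will be too small. The documents do not support that. They name no test, and a Wald test stays near its level; only a likelihood-ratio test would be liberal, by about one percentage point with three terms.

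A reader might also take the seven-term figures as describing the plan. They do not. Those figures need all four severity scores to differ between arms, and even then the scores are only to be considered.

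Nor can one say that the reported odds ratio will overstate the benefit. The exaggeration is an average over repeated trials with a real effect.

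The stakes should not be inflated either. Section 3(a) calls the data preliminary, and section 10(a) makes roll-out depend on replication in independent samples.

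It is also fair to say that fixing the covariates at three and naming the Wald test would deal with the p-value and the larger biases. The three-term bias in the estimate would remain.

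**Conclusion.** The point holds for Primary 1a as a cheap improvement. If treatment works, ordinary maximum likelihood with the three fixed terms exaggerates the log odds ratio by about 11 to 16% on average, and by more as severity scores are added. With no effect there is no bias in the estimate.

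This rests on four assumptions: that unqualified logistic regression means maximum likelihood; that the background 60% relapse rate applies to sham; that active relapse is 30 to 40% when treatment works; and that covariates are independent with modest effects. Fewer evaluable people would make it worse. With N = 32 (an assumed 20% loss), likelihood-ratio type I error is 6.5% with three terms.

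A reader might extend the point to the Cox model in 1b ("Primary Hypothesis 1b will be tested with Cox regression"). The evidence is not firm enough to ask for a change there. Simulated hazard-ratio bias with three terms is smaller (log hazard ratio about -0.86 against -0.80), and separate simulations of the likelihood-ratio error rate disagree (5.5% against 6.3 to 6.8%). A re-randomisation p-value would leave the hazard-ratio bias in place.

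**What to change.** In the Statistical Analyses Plan, under Primary Hypothesis 1a and Exploratory Hypotheses 1a and 2a, state that the logistic model is fitted by Firth penalised likelihood, with profile penalised-likelihood confidence intervals and the penalised likelihood-ratio test for the treatment term, whatever covariate set is used. This also settles the unnamed test and gives a finite estimate if separation occurs.

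The cost is a sentence of SAP wording and an established but non-default software routine. No extra participants or data are needed. With three terms, apparent power is a few points below that of the liberal likelihood-ratio test and about equal to that of the Wald test. Leave 1b unchanged on this account.
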